#### **8.6.2.2 Duration of Response (DOR) and Progression-Free Survival (PFS)**

Time-to-event endpoints including DOR and PFS will be summarized descriptively using the Kaplan-Meier method. The Kaplan-Meier estimates of the median DOR and PFS and the corresponding 2-sided 95% confidence intervals, calculated using the method of Brookmeyer and Crowley, will be presented by tumor type, treatment regimen and in total. Also, the Kaplan-Meier estimates of ongoing response rate and PFS rate along with the corresponding 2-sided 95% confidence intervals will also be provided by 3 months intervals (3, 6, 9 months, etc.), split by tumor type, treatment regimen and for overall. Plots of the Kaplan-Meier estimate of the survival function over time for ongoing response rate and PFS rate will be generated with number of subjects at risk noted by 3 months intervals, grouped by tumor type and treatment regimen. Similar analyses may be repeated for ongoing response rate but split by response type (CR/CRi versus PR) instead of tumor type for assessing difference in median relapsed time and/or ongoing response rate (by 3 months intervals) between complete and partial responders.

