4.13. Discontinuation of Voruciclib Administration

Subjects may continue to receive voruciclib monotherapy or voruciclib + venetoclax combination therapy provided there is evidence of clinical response (PR or better) by the end of Cycle 6. Subjects may discontinue voruciclib monotherapy or voruciclib + venetoclax combination therapy for reasons including the following:

- Documented progression of disease while receiving therapy
- Unacceptable AE(s) considered secondary to voruciclib despite appropriate therapy and/or dose modification
- Intercurrent illness that precludes continued study therapy
- Withdrawal of consent by the subject
- Changes in the subject's medical condition that render further administration of voruciclib unacceptable in the judgment of the Principal Investigator or sponsor
- Treatment of the disease with another therapeutic regimen
- Pregnancy or breastfeeding
- Substantial noncompliance with study procedures
- Termination of study by the sponsor

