8.6. Treatment

The treatment phase begins on the day voruciclib or venetoclax is first administered and continues through the last day of administration. Treatment will be tracked by 28-day periods identified by a numerical cycle (e.g., Cycle 1, Cycle 2...). Response assessments for subjects with CLL/SLL, FL, MCL, MZL, DLBCL, and high-grade B-cell lymphomas, as defined in [Section 7](#), will be performed according to the Schedule of Assessments ([Appendix 1](#)) and detailed in [Appendix 5](#) and [Appendix 6](#). Response assessments for subjects with AML will be performed according to the Schedule of Assessments ([Appendix 2](#) and [Appendix 3](#)) and detailed in [Appendix 4](#).

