8.7. End of Study Visit

The End of Study (EOS) visit will occur 30 days (± 3 days) from the last day of treatment drug(s) administration (or prior to starting a new treatment if urgent treatment is required). The end of treatment date and reason for discontinuation study drugs will be entered in the End of Treatment form in the EDC.

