8.8. End of Study

The study will be closed when all subjects who received study drug have completed their EOS visit and all study data have been collected for analysis.

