**Table 3-3 Cohorts with Combination Voruciclib + Venetoclax in Amendment 12**

| Cohort Dose Level | Doses and Schedule   |
|--------------------------|---|
| 12                       | voruciclib 50 mg QOD, administered IS 2w,2w + venetoclax administered QD × 28 days |
| 13                       | voruciclib 50 mg QD, administered IS 2w,2w + venetoclax administered QD × 28 days  |
| 14                       | voruciclib 100 mg QD, administered IS 2w,2w + venetoclax administered QD × 28 days |
| 15                       | voruciclib 150 mg QD, administered IS 2w,2w + venetoclax administered QD × 28 days |
| 16                       | voruciclib 200 mg QD, administered IS 2w,2w + venetoclax administered QD × 28 days |
| 17                       | voruciclib 250 mg QD, administered IS 2w,2w + venetoclax administered QD × 28 days |
| 18                       | voruciclib 300 mg QD, administered IS 2w,2w + venetoclax administered QD × 28 days |
| 19                       | voruciclib 350 mg QD, administered IS 2w,2w + venetoclax administered QD × 28 days |
| 20                       | voruciclib 150 mg QD, administered IS 3w,1w + venetoclax administered QD × 28 days |

Dose escalation proceeds until a real-time assessment of clinical and PK parameters by the SRC establishes the safe and mBED for voruciclib in combination with venetoclax. More specifically, a voruciclib dose in combination with venetoclax that meets the following criteria:

- DLT not to exceed 1 in 6 subjects, overall response rate (ORR)  $\geq 30\%$ , as compared to historical ORR of 19% with 400-800 mg venetoclax alone in relapsed/refractory AML, and
- Trough plasma concentration of 1 to 1.5  $\mu\text{M}$ , concentrations shown to be synergistic in combination with venetoclax in preclinical models.

Once the safe and mBED of voruciclib in combination with venetoclax is identified by the SRC, which could be a dose less than 350 mg, dose escalation will stop. The subjects still actively dosing in the prior cohort may have their dose escalated to the next dose level after completing Cycle 1 (intra subject dose escalation). Subjects may continue to receive voruciclib plus venetoclax while there is evidence of clinical benefit (partial remission [PR] or better) by the end of Cycle 6 and acceptable toxicity as judged by the Investigator.

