### **3.1.6 Discontinuation of Voruciclib Administration**

Subjects may continue to receive voruciclib for up to 19 cycles (approximately 18 months). After this period, if there is continuing evidence of clinical benefit and acceptable toxicity as judged by the Investigator, following discussion with the Medical Monitor, the subject may be allowed to receive additional cycles. Subjects may discontinue voruciclib for reasons including the following:

- Documented progression of disease while receiving therapy
- Unacceptable AE(s) considered secondary to voruciclib despite appropriate therapy and/or dose modification
- Intercurrent illness that precludes continued study therapy
- Withdrawal of consent by the subject
- Changes in the subject's medical condition that render further administration of voruciclib unacceptable in the judgment of the Principal Investigator or sponsor
- Treatment of the disease with another therapeutic regimen
- Pregnancy or breastfeeding
- Substantial noncompliance with study procedures
- Termination of study by the sponsor

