**Table 5-2: Date of Progression or Censoring for PFS**

| Situation  | Date of progression or censoring   | Outcome  |
|--|--|----------|
|  |  |          |
| Death or disease progression   | Date of death or first disease assessment (planned or unplanned) showing disease progression, whichever occurs first | Event    |
| No evaluable disease assessments   | Date of the first dose   | Censored |
| Subsequent anticancer treatment started before the first documented disease progression or death | Date of last disease assessment prior to the subsequent anticancer treatment   | Censored |
| Alive and without disease progression on or before EOS visit                                     | Date of last disease assessment  | Censored |

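### PFS rates at 9 months and later will rest on responders only, because subjects without PR by the end of Cycle 6 leave the risk set at about month 5.5 to 6.5 and are censored

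*SAP*

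**What the plan says.** - **Continuation.** Protocol 4.13 allows treatment to go on "provided there is evidence of clinical response (PR or better) by the end of Cycle 6". SAP 3.1.1 (below Table 3-3) repeats this for the combination: "while there is evidence of clinical benefit (partial remission [PR] or better) by the end of Cycle 6". SAP 3.1.6 differs and sets no PR condition: "Subjects may continue to receive voruciclib for up to 19 cycles (approximately 18 months".
- **Follow-up.** Protocol 8.6: "Treatment will be tracked by 28-day periods". Protocol 8.7: "The End of Study (EOS) visit will occur 30 days" after the last dose, with a window of 3 days either way. Protocol 8.8: "The study will be closed when all subjects who received study drug have completed their EOS visit". Appendices 1 to 3 schedule no progression or survival follow-up after that visit.
- **Censoring.** SAP Table 5-2 has the row "Alive and without disease progression on or before EOS visit", with the date of the last disease assessment as the censoring date. Protocol 10.6 agrees.
- **Reporting.** SAP 8.6.2.2 gives PFS medians and rates; the rates "will also be provided by 3 months intervals (3, 6, 9 months, etc". They are split by tumor type and regimen and shown overall, but not by response status. The analysis set (SAP 6.3, 8.6.2) includes non-responders. No time limit, landmark analysis or sensitivity analysis is specified.

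**The concern.** Kaplan-Meier assumes that a censored subject has the same future risk as those who remain under observation at that time. Here the remaining group is selected on response. A subject with stable disease at the end of Cycle 6 stops, has one more visit and is censored. A responder stays on treatment and under assessment. From then on the curve falls at the responders' rate, and that rate is applied to the censored subjects as well.

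PFS is a named secondary endpoint (Protocol 10.2). A 9- or 12-month rate in the study report would be read as the PFS of the treated population, although nobody without a response was observed at those times.

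**Working it through.** The documents state no PFS rate, so there is no plan figure to reproduce.

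**1. When non-responders leave** (28-day cycles; days divided by 30.4375, as in SAP 5.1.2)
- End of Cycle 6: 6 × 28 = Day 168, month 5.52. Cycle 7 Day 1: Day 169, month 5.55.
- Combination, venetoclax to Day 168: final visit Day 198 ± 3 = Days 195-201, months 6.4-6.6.
- Monotherapy two weeks on/two off, last dose Day 154: Days 181-187, months 5.9-6.1.
- Monotherapy one week on/three off, last dose Day 147: Days 174-180, months 5.7-5.9.

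Absent dose delays, nobody stopped for lack of PR is at risk at month 9.

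**2. Size of the effect.** Assumptions, not from the documents: exponential PFS, median mR in responders (share p) and mN in non-responders, all non-responders censored at month c.
- True PFS: S(t) = p·exp(−ln2·t/mR) + (1−p)·exp(−ln2·t/mN)
- Kaplan-Meier limit after c: K(t) = S(c)·exp(−ln2·(t−c)/mR)

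Worked case: p = 0.30 (the ORR threshold in SAP 3.1.1), mR = 15, mN = 4, c = 6.5.
- S(6.5) = 0.222 + 0.227 = 0.449. Non-responders are 0.227/0.449 = 51% of those still at risk, and all of them are removed.
- Month 9: K = 0.449 × 0.891 = 40%; S = 0.198 + 0.147 = 35%.
- Month 12: K = 0.449 × 0.776 = 35%; S = 0.172 + 0.087 = 26%.
- With c = 5.5, S(5.5) = 0.503, and K is 43% at month 9 and 37% at month 12.

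**3. Range of the excess at month 12**

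| Assumptions | Excess (points) |
|---|---|
| p 0.2-0.4, mR 12-15, mN 3-6, c 5.5 or 6.5 | 5.6 to 12.9 |
| p 0.3, mR 4, mN 2, c 6.5 | 1.7 (6.6% against 4.8%) |
| p 0.3, mR 4, mN 2, c 5.5 | 2.3 (7.1% against 4.8%) |
| equal medians (9 and 9) | 0 |

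The low end of the first row is at p = 0.4, mR = 12, mN = 6, c = 6.5. The high end is at p = 0.2, mR = 15, mN about 4.2, c = 5.5.

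**4. Check by simulation.** With 68 subjects (the planned combination total, Protocol 10.1), p = 0.30, medians 12 and 4, c = 6.5 and 3,000 runs, the mean Kaplan-Meier rates were 37.6% and 31.6% at months 9 and 12. The formula gives 37.5% and 31.5%; true PFS is 32.6% and 23.7%. About 12 subjects were at risk at month 9, all responders.

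**5. What the event-counting analysis would show.** In the worked case, treating a Cycle 6 stop as an event leaves only the responder term: 17.2% at month 12. The true 26.0% then lies between 17.2% and the planned estimate of 34.8%.

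**The case against.** - **The rule is permissive and not uniform.** Protocol 4.13 says subjects may continue under a condition, and its list of reasons for stopping does not name lack of PR. SAP 3.1.6 has no PR condition, and SAP 3.1.1 also carries a general benefit-based statement without one. A reader might infer that every stable-disease subject is censored by rule. The texts do not support that across the whole study. The monotherapy cohorts, which include all B-cell subjects, were complete at Amendment 12, and the documents do not show which rule governed them. For the combination cohorts Protocol 4.13 and SAP 3.1.1 agree, so the point stands there.
- **The direction is not guaranteed.** A reader might infer that the bias always favors voruciclib. The documents give no hazards. The bias is nil if hazards are equal or if no non-responder is progression-free at Cycle 6. Short medians are plausible in AML: Protocol section 1 cites a median response duration of 48 days for venetoclax alone, in a mostly relapsed or refractory series. This limits the size of the bias. Even where it is small, the later rates still come from responders only.
- **The stakes are modest.** PFS is secondary and descriptive, the study is declared exploratory (SAP 7.9), and the combination dose is chosen on DLTs, ORR and trough concentration. Nothing here affects dose selection. Numbers at risk every 3 months will show the drop, but not that those remaining are all responders.
- **Medians.** A reader might infer that median PFS is inflated too. In the worked case with censoring at month 6.5, S(6.5) is already 45%, so the median is reached first and is unaffected. Only a median reached after the censoring would be affected.

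Duration of response is calculated in responders only and is not touched by this mechanism.

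**Conclusion.** The concern holds as a conditional statement. Where the Cycle 6 PR rule applies, and absent dose delays, the all-subject PFS rates at 9 months and later are responder rates in all but name. They overstate PFS if non-responders still progression-free at Cycle 6 would progress sooner than responders, which is the usual expectation but is not shown in the documents. Under the stated exponential assumptions the 12-month excess is about 6 to 13 points, about 2 points with medians of 4 and 2 months, and zero with equal hazards. Medians reached before the censoring are sound. The 6-month rate falls between the Cycle 7 Day 1 assessment (month 5.55) and the combination end-of-study visit (months 6.4-6.6), so it may be slightly affected, depending on which assessment is the last.

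Separately, SAP 3.1.6 contradicts both Protocol 4.13 and SAP 3.1.1. If different subjects stopped under different rules, the pooled PFS curve mixes two censoring patterns.

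**What to change.** In SAP 8.6.2.2:
1. Report all-subject Kaplan-Meier PFS rates only through the Cycle 7 Day 1 assessment, including its visit window (about month 5.5-6). By the schedule the window runs from 7 days before to 2 days after Day 169, so it closes on Day 171, month 5.6. A cut at Day 168 would lose progressions found at an on-time Cycle 7 Day 1 visit.
2. Show later PFS only as a landmark analysis of subjects in PR or better at that assessment, labelled as conditional on response.
3. Add a sensitivity analysis in which stopping for lack of PR at Cycle 6 counts as a PFS event.
4. Reconcile SAP 3.1.6 with Protocol 4.13 and SAP 3.1.1, and state which continuation rule governed each completed cohort.

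The cost is SAP wording and one extra table, with no change to study conduct. The small downside is that no all-subject PFS rate is quoted beyond about month 6.

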- u. Dispense study drug** – Voruciclib is administered orally once a day on an empty stomach at least 1 hour prior to food or 2 hours after food at approximately the same time each day. On days of PK sampling, subjects should be instructed not to take voruciclib until after the PK sample is collected (note that in Amendment 7, there is no dosing on Day 8 for the IS_{1w3w} and Day 15 for the IS_{2w,2w}). A compliance diary assessment and returned voruciclib drug accountability should be performed at each visit which includes voruciclib dispensing.

As of Amendment 7, voruciclib will be administered on an intermittent dosing schedule of 2 weeks on/2 week off (IS_{2w,2w}) or 1 week on/3 weeks off (IS_{1w,3w}), in the 28-day cycle. Note that voruciclib is taken daily on dosing days only, i.e., Days 1 through 14 for IS_{2w,2w}, and on Days 1 through 7 only on the IS_{1w,3w} regimen.

- v. PK sampling** – Pre-dose specimens should be within 2 hours of dosing and for post-dose within \pm 30 minutes) after dosing.
Cohorts 1-5:

- Cycle 1 Day 1: pre-dose (before voruciclib dose is taken); and at 4- and at 6- hours post-dose
- Cycle 1 Day 2: pre-dose (i.e., 24 hours after the Cycle 1 Day 1 voruciclib dose)
- Cycle 1 Day 8: pre-dose (24 hours after the preceding last dose, before voruciclib is taken)
- Cycle 1 Day 15: pre-dose (before voruciclib dose is taken); at 4- and at 6- hours post dose

Cohorts 6b-11b (IS dosing):

- Cycle 1 Day 1: pre-dose and at 4- and at 6- hours post-dose
- Cycle 1 Day 2: pre-dose (24 hours after the preceding last dose)
- Cycle 1 Day 8: pre-dose (24 hours after the preceding last dose)
- Cycle 1 Day 15: (24 hours after the preceding last dose), if applicable [Day 15 samples only collected for the IS_{2w,2w} schedule]
- Cycle 2 Day 1: pre-dose

- w. Disease assessment** – Scans, bone marrow aspirate/biopsy and laboratory evaluation as appropriate for individual subjects. Scans to be performed at baseline within 3 months of Cycle 1 Day 1 and after termination of prior therapy, Cycle 3 Day 1, Cycle 7 Day 1, every 6 cycles thereafter, and upon permanently stopping study treatment. Response assessments for CLL/SLL and FL and other B-cell lymphomas, refer to [Appendix 5](#) and [Appendix 6](#), respectively.

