APPENDIX 3. SCHEDULE OF ASSESSMENTS - AML SUBJECTS ONLY – COMBINATION THERAPY (CONTINUED)

- p. Coagulation** – aPTT, PT, and INR.
- q. Urinalysis** – Dipstick.
- r. Baseline chest x-ray** – recommended if the subject has not had recent chest imaging.
- s. Issue and Assess Compliance Diary** – Assess returned diaries for study drug dosing compliance. New compliance diary to be dispensed with each dispensing of study drug.
- t. Dispense study drug** – Venetoclax is administered orally once daily to be taken with food and water. Voruciclib is administered orally once a day on dosing days, at least 2 hours after venetoclax. On days of PK sampling (for PK sampling schedules refer to [Section 9.14.2](#)), subjects should be instructed to not take venetoclax or voruciclib until after the pre-dose PK sample is collected.
- As of Amendment 11, voruciclib will be administered on an intermittent dosing schedule of 2 week on/2 week off (IS_{2w,2w}) in the 28-day cycle. Note that voruciclib is taken once daily on dosing days only (i.e., Days 1 through 14 on IS_{2w,2w}), with the exception of Cohort 12 which is taken every other day (i.e., Days 3, 5, 7, 9, 11, and 13 of Cycle 1 and Days 1, 3, 5, 7, 9, 11, and 13 of Cycle 2 and beyond).
- As of Amendment 12, voruciclib will be administered on an intermittent dosing schedule of 3 weeks on/1 week off (IS_{3w,1w}) in the 28-day cycle for Cohorts 21–25. Voruciclib is taken once daily on dosing days only (i.e., Days 1 through 21 on IS_{3w,1w}).
- u. Disease assessment / Bone marrow** – Bone marrow aspirate/biopsy and laboratory evaluation at screening (up to 28 days prior to starting venetoclax), Cycle 2 Day 1, and Day 1 of every subsequent cycle until a CR or CRi is achieved. Thereafter when bone marrow examinations are obtained as clinically indicated, and at EOS. Both biopsy and aspirate are recommended for disease assessment, but biopsy may be omitted if aspirate is considered to be sufficient. Bone marrow assessment may be omitted if the subject has clear evidence of disease progression based of peripheral blood count/blasts analysis. Bone marrow aspirate sample collected at the time of disease assessment may be used for exploratory biomarker analysis in bone marrow/bone marrow aspirate. If any remaining sample is available after evaluation for disease assessment. it should be submitted to the central laboratory for pharmacodynamic biomarker/correlative study (refer to the Lab Manual).

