- ⁱ Lymphocytosis can be prominent early during treatment and can persist over time, and should not be confused with disease progression in subjects who otherwise have persistent disease control. In the absence of other objective evidence of disease progression, the occurrence of lymphocytosis will not preclude subjects from meeting the criteria for PR if other criteria for PR are met, and will not be considered evidence of CLL progression if occurring in isolation.

The goal of confirmation of objective response is to avoid overestimating responses. In cases where confirmation of response is not feasible, it should be made clear when reporting the outcome that the response(s) is (are) not confirmed.

For subjects experiencing disease progression due to Richter's Syndrome while on study, supplemental data may be collected.

To be assigned a status of PR or CR, changes in tumor measurements must be confirmed by repeat assessments that should be performed at least 2 months after the criteria for response is first met. Bone marrow biopsy and aspirate to confirm CR must be obtained at least 2 months after other criteria for CR are first met.

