#### 5.1.2 Secondary Efficacy Endpoints

Secondary efficacy endpoints (within each tumor type: AML and B cell malignancies) are as follows:

- Overall Response Rate (ORR), defined as the proportion of subjects who achieve a best overall response of
  - CR, CRi, or PR, with responses defined per 2008 International Workshop on CLL (IWCLL) guidelines,
  - CR or PR by 2014 Lugano criteria for non-Hodgkin lymphoma,
  - CR, CRi, CRMRD, MLFS by the 2017 ELN criteria for AML
- Estimates of the exposure and association with efficacy variables for voruciclib administered as monotherapy, and for voruciclib and venetoclax when administered in combination
- Duration of Response (DOR) defined as the time from first achieving a response to date of documented disease progression or death from any cause. Subjects who die due to any cause prior to progression will be censored. DOR will be calculated as follows for subjects who have a best overall response of CR/CRi or PR:

$$\text{DOR (months)} = (\text{Progression/Censoring Date} - \text{Response Start Date} + 1) / 30.4375$$

Subjects meeting at least one of the following criteria will be right-censored for DOR:

- death due to any cause prior to disease progression
- subsequent anticancer therapy without documented disease progression
- alive and without documented disease progression on or before the EOS visit

If a subject meets more than one of these criteria, then the scenario that occurs first will be used for the analysis. The progression or censoring date will be determined based on the conventions listed in Table 5-1.

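### Splitting duration of response by best response (CR/CRi versus PR) favours complete responders within a tumor type even when depth of response has no effect

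*SAP*

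**What the plan says.** - **The split.** SAP 8.6.2.2 plans Kaplan-Meier medians and 3-monthly rates for DOR and PFS by tumor type and treatment regimen. It then adds an option for DOR: "Similar analyses may be repeated for ongoing response rate", "split by response type (CR/CRi versus PR) instead of tumor type for assessing difference in median relapsed time and/or ongoing response rate". The section names no test; the endpoints "will be summarized descriptively using the Kaplan-Meier method".
- **The clock.** SAP 5.1.2: "Duration of Response (DOR) defined as the time from first achieving a response to date of documented disease progression or death from any cause".
- **The label.** SAP 5.1.2: "DOR will be calculated as follows for subjects who have a best overall response of CR/CRi or PR". SAP 8.6.2.1 also works from best response. SAP 8.6.2.2 does not say how response type is assigned in the split, and no other CR/PR label is defined.
- **Later chances to be relabelled.** For combination AML, Protocol Appendix 3 footnote u schedules marrow at "Cycle 2 Day 1, and Day 1 of every subsequent cycle until a CR or CRi is achieved". For B-cell disease, Appendix 1 footnote w schedules scans at "Cycle 3 Day 1, Cycle 7 Day 1, every 6 cycles thereafter, and upon permanently stopping study treatment". Appendix 6, Table 21 footnote a, adds a CT at Cycle 5 for lymphoma.
- **Status.** SAP 7.9 calls the study exploratory.

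**The concern.** The groups are formed on something that happens after time zero. To be upgraded from PR to CR/CRi, a subject must still be in response at the next assessment, so part of that subject's DOR is guaranteed by the label. Early progressors have no such chance and collect in the PR group. This is guarantee-time (immortal-time) bias. It sits in the medians and the 3-monthly rates themselves, so calling the analysis descriptive does not remove it.

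The stated purpose is to assess a difference between complete and partial responders. A reader of the resulting curves would probably take a longer CR/CRi curve as evidence that deeper responses last longer, which the split as written cannot show.

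**Working it through.** The documents give no sample size, expected DOR or conversion rate for this split, so there is no planned figure to reproduce. The check asks what the split shows when depth has no effect.

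**Length of the wait.** One cycle is 28/30.4375 = 0.92 month.
- AML: one cycle, 0.92 month.
- B-cell: from Cycle 3 to Cycle 7 is four cycles, 3.68 months (Appendix 1). From Cycle 3 to Cycle 5 is two cycles, 1.84 months (Table 21 footnote a).

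**Model.** Every responder has the same exponential DOR, S(t) = exp(−t·ln 2/m). A fraction f is in CR/CRi at first response. At later visit j, at time v_j, each PR still in response is upgraded with probability p. Then:
- Share labelled CR/CRi: P = f + Σ (1−f)·p·(1−p)^(j−1)·S(v_j)
- CR/CRi curve: [f·S(t) + Σ (1−f)·p·(1−p)^(j−1)·S(max(t, v_j))] / P
- PR curve: [S(t) − numerator of the CR/CRi curve] / (1−P)

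The values of m, f and p are assumptions.

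**Worked AML case: m = 3, f = 0.3, p = 0.10, six later monthly visits.**
- S at the six visits: 0.8085, 0.6537, 0.5285, 0.4273, 0.3455, 0.2794.
- Weighted by 0.9^(j−1): 0.8085 + 0.5883 + 0.4281 + 0.3115 + 0.2267 + 0.1650 = 2.528.
- P = 0.3 + 0.7 × 0.10 × 2.528 = 0.477.
- At 3 months S = 0.50. The first three visits have passed, so the numerator is 0.3 × 0.50 + 0.07 × [(1 + 0.9 + 0.81) × 0.50 + 0.3115 + 0.2267 + 0.1650] = 0.294.
- Ongoing at 3 months: CR/CRi 0.294/0.477 = 62%; PR (0.500 − 0.294)/0.523 = 39%. The truth is 50% in both.

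**Large-sample medians (months), no effect of depth:**

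| Setting | f | p | True | CR/CRi | PR |
|---|---|---|---|---|---|
| AML, monthly | 0.3 | 0.10 | 3 | 4.07 | 2.20 |
| AML, monthly | 0.2 | 0.17 | 3 | 4.59 | 1.76 |
| B-cell, upgrades at C7 and C13 | 0.3 | 0.30 | 6 | 8.40 | 4.05 |
| B-cell, upgrades at C7 and C13 | 0.2 | 0.50 | 6 | 9.55 | 3.01 |
| B-cell, with C5 added | 0.3 | 0.30 | 6 | 7.85 | 3.40 |
| B-cell, with C5 added | 0.2 | 0.50 | 6 | 8.21 | 1.91 |
| Any, no upgrades | any | 0 | m | m | m |

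A wider AML range (f from 0 to 0.5, p from 0.10 to 0.30, true median 3, monthly visits throughout follow-up) gives 3.8 to 6.5 for CR/CRi versus 1.2 to 2.0 for PR.

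**Alternatives on the same null.** Grouping by first response returns the true median in both groups. So does a landmark at a fixed time: at 1.84 months in AML with a true median of 3, it gives 3.0 versus 3.0 and keeps S(1.84) = 65% of responders. CR/CRi as a time-dependent status gives a rate ratio of 1.00.

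**Pooling.** Suppose AML PR does not count as a response, so all AML responders are CR/CRi. Take 10 AML responders with a median of 48 days (48/30.4375 = 1.58 months, the historical venetoclax figure in Protocol section 1) and 5 B-cell responders with a median of 6 months, f = 0.25, p = 0.30 and upgrades at C7 and C13. The pooled medians are about 2 months for CR/CRi and 4 for PR: the direction reverses. With an AML median of 3 they are about 3.7 and 4.

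**The case against.** The strongest reply is that this is an optional, descriptive display of a secondary endpoint in an exploratory Phase 1 study, with no test and no stated role in dose selection. That stands, and it limits the weight of the point. It does not make the comparison unbiased.

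Grouping by best overall response is also an inference, since SAP 8.6.2.2 says only response type. The inference is reasonable because the SAP defines no other label, and the fix resolves it either way.

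Three stronger readings are tempting, and the documents do not support them.
- **That complete responders will look more durable in the reported split.** This holds within a tumor type. The split replaces tumor type, so diseases are pooled, and the pooled direction can go either way.
- **That the trial faces a high false-positive rate.** No test is planned. A rate computed for, say, 20 B-cell responders describes a trial that cannot occur. Monotherapy closed at 40 subjects (Protocol 10.1). At least 4 + 3 × 3 + 6 = 19 were AML (Cohort 2; Cohorts 6a, 7a and 8a; the expansion), leaving at most 21 B-cell. The 8 in Cohort 1 were all B-cell, and 50 mg QD gave no objective responses (Protocol 4.2.1.1). At most about 13 B-cell responders remain.
- **That B-cell subjects must wait four cycles.** Table 21 footnote a allows two.

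The CLL/SLL rule "Bone marrow biopsy and aspirate to confirm CR must be obtained at least 2 months after other criteria for CR are first met" might seem to lengthen the wait further. No weight is put on it, because Appendix 5 asks for repeat assessment of PR as well.

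**Conclusion.** The point holds in limited form. Within a tumor type, the SAP's clock and label together bias the optional split towards CR/CRi. The direction follows from the definitions and needs only that some PRs are later upgraded. The size does not follow from the documents: it rests on an exponential DOR common to all responders and on assumed values for its median, the share in CR/CRi at first response and the conversion rate. Under the AML assumptions above, the apparent median is about twice as long or more in CR/CRi (4.07/2.20 = 1.9; 4.59/1.76 = 2.6) when the truth is equality.

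Two matters in the documents bear on the same analysis:
- SAP 5.1.2 leaves PR out of the AML response rate (CR, CRi, CR without MRD, MLFS), while its DOR rule and SAP 8.6.2.1 include PR. The AML PR group is therefore undefined, and MLFS responders have no place in the split.
- Appendix 1 footnote w and Table 21 footnote a give different lymphoma scan schedules, which must be reconciled.

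**What to change.** In SAP 8.6.2.2, state that if this split is produced, responders are grouped by the category of their first documented response, within tumor type, and that DOR from first response is not split by best overall response. State also whether PR counts as a response in AML and where MLFS belongs.

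This costs a few sentences and a small programming change, and no responder is dropped. The drawback is that it describes depth at first response rather than best depth, in small groups.

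If best depth is of interest, either treat CR/CRi as a time-dependent status, or prespecify a landmark at a fixed time after first response. With the landmark, keep only subjects still in response, class them by best response to that date and count DOR from there; subjects who progress earlier are lost. Do not define the AML landmark by a count of post-response assessments such as the third, because scheduled marrows stop once CR/CRi is reached. Dropping the optional split is also acceptable.
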